1.6.1 Phase 2 recruitment

Participants into phase 2 of the study will be invited from the cohort of patients who have already undergone investigations for suspected prostate cancer which include MRI imaging as a requisite. Patients who have low probability MRI scores of PI-RADS 1 or 2 will be invited onto the phase 2 longitudinal arm of the study. Patients who have had biopsy and have either low risk localised

prostate cancer and have elected to be monitored with AS, or those with higher grade disease and who have elected to be monitored via a WW pathway will also be invited on to the phase 2 longitudinal arm of the study.

1.6.2 Sample size phase 2

Again, determining a sample size for this proof of concept study remains difficult. Given the small numbers likely to be recruited into phase 1 and therefore eligible to continue to phase 2, all phase 1 participants who are managed under AS or WW will be invited to continue onto phase 2 of the study with maximum cohort of 30 being accepted. It is acknowledged that inclusion in phase 2 is dependent upon cancer grading at diagnosis and, due to uncertainty of disease diagnosis within the cohort it may be difficult to recruit participants within the two-year time limit for data collection. Participants in phase 1 and 2 will continue to be recruited up to a maximum of 18 months from the commencement of the study to maximise the opportunity for phase 2 recruitment.

1.6.3 Inclusion criteria for phase 2

Men referred to urology within Hull University Teaching Hospitals NHS Trust with known localised prostate cancer of Gleason 3 + 3 (6) or less and:

- Are eligible for an AS monitoring pathway
- Are on an AS monitoring pathway which is regularly reviewed by a consultant urologist
- Able to attend Castle Hill Hospital for 6 monthly multi-parametric US examinations
- Are able to tolerate a rectal ultrasound examination
- Able to provide informed consent to the study

1.6.4 Exclusion criteria for phase 2

- Men who meet eligibility criteria for active surveillance but have elected to undergo active treatment (hormone treatment, prostatectomy or radiotherapy)
- Men who do not meet eligibility criteria for active surveillance
- Men who are eligible for inclusion but who cannot tolerate rectal ultrasound examinations.
- Men who are unable to consent to the study
- Men who withdraw consent during the longitudinal study
- Men who are unable to attend Castle Hill Hospital for ultrasound imaging within study time frames

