1.4 Study phases

This study is being undertaken as a PhD research project but within the NHS care setting. The study will consist of four phases:

1.4.1 Phase 1:

In this initial phase, eligible men who have consented to participate will undergo a transrectal ultrasound examination with a standard ultrasound probe and, at the same attendance a transrectal ultrasound examination with a new and novel probe using 29MHz scanning frequency. The images obtained from this examination will be retrospectively compared with the MRI imaging that has been obtained as part of the standard care pathway. The images obtained will be reviewed by two

health care practitioners with experience in prostate imaging and the outcomes of these reviews compared to evaluate agreement levels.

1.4.2 Phase 2:

The second phase of the study will evaluate the use of multiparametric standard and micro ultrasound in the assessment of men who are on an AS or WW pathway. This phase the study will evaluate if there are any changes in the findings at repeat ultrasound examinations that can indicate disease progression. Eligible men, who have consented to participate, will again undergo a transrectal ultrasound examination with a standard ultrasound probe and, at the same attendance a transrectal ultrasound examination with a new and novel probe using 29MHz scanning frequency.

1.4.3 Phase 3:

The process and acceptability of implementing new interventions and technologies into everyday clinical practice is frequently overlooked following research trials. This third phase will explore the views of the health care practitioners, who have consented to participate, regarding the use and implementation of the proposed new technologies; skill mix between these professional groups will be required for successful long term practice. The participants will be recruited from differing professionals within the staff groups of Hull University Teaching Hospitals NHS Trust. An adapted survey tool, derived from normalisation process theory framework, will be used to better understand how and if the new, complex, multi-parametric ultrasound techniques can be implemented within the organisational setting of everyday routine practice. A baseline assessment of confidence in knowledge and skills related to prostate cancer evaluation using ultrasound will be made.

1.4.3.1 Staff training:

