1.5.2 Eligibility criteria in clinical practice

MRI is offered to all men who meet the eligibility criteria of age ≤ 75 , PSA ≤ 20 and life expectancy of ≥ 10 years. MRI is reported using the PI-RADS V2 criteria; a 5 point scale with 1 & 2 highly unlikely to have significant prostate cancer, 4 & 5 highly likely to have significant prostate cancer and PI-RADS 3 equivocal and further investigation warranted. The pathway in the Hull University Teaching Hospitals NHS Trust is that patients with PI-RADS score of 1 or 2 are not routinely offered biopsy due to the risk of biopsy complications being greater than the likelihood of prostate cancer. Men meeting these criteria will be invited to participate in phase 1 of the study and the multi-parametric US will be correlated with MRI only. A biopsy will not be performed. Any men from this cohort electing for AS will be invited to join phase 2.

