1.6.5 Phase 2 recruitment process

Once the initial diagnosis has been made, patients are discussed at the urology prostate multi-disciplinary meeting. A decision is made as to the most appropriate course of treatment is made and, following this, the patients attend for a consultation within a specialist prostate cancer clinic. Biopsy results and MDT outcomes are discussed and the patient is given the advised options for management. For localised low risk disease this does include active surveillance. For patients who may be less eligible for active or even deferred treatment an option of watchful waiting prior to palliative treatment being given can be offered. Providing all patients within these cohorts have had pre-biopsy MRI they are eligible for the study.

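### Phase 2 recruitment text (1.6.1) invites PI-RADS 1–2 men and higher-grade watchful-waiting men whom the phase 2 criteria (1.6.3, 1.6.4) do not admit

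*Protocol*

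**What the plan says.** The protocol describes the phase 2 population in several places, and the descriptions differ.

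- **1.6.1 (recruitment)** invites three groups. The first is men with a low-probability MRI: "Patients who have low probability MRI scores of PI-RADS 1 or 2 will be invited onto the phase 2" longitudinal arm, with no further condition. The second is biopsied men with low-risk localised cancer who chose AS. The third is "those with higher grade disease and who have elected to be monitored via a WW pathway".
- **1.5.2** also provides for PI-RADS 1–2 men, but more narrowly: "Any men from this cohort electing for AS will be invited to join phase 2". It notes that "patients with PI-RADS score of 1 or 2 are not routinely offered biopsy" and that no biopsy is done in phase 1 for these men.
- **1.4.2** sets phase 2 "in the assessment of men who are on an AS or WW pathway". **1.6.2** says "all phase 1 participants who are managed under AS or WW will be invited to continue onto phase 2 of the study", up to a maximum of 30. **1.6.5** describes the AS and WW routes and then states: "Providing all patients within these cohorts have had pre-biopsy MRI they are eligible for the study". None of these three sections names PI-RADS 1–2 men.
- **1.6.3 (inclusion)** requires "known localised prostate cancer of Gleason 3 + 3 (6) or less", eligibility for AS, and being on an AS pathway reviewed by a consultant urologist. **1.6.4 (exclusion)** removes men who do not satisfy the AS criteria.
- The aim (**1.2**), the primary objective (**1.3.1**), the opening of **1.6** and the consent text (**1.9.2**) mention AS and not WW.

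**The concern.** Eligibility criteria decide who may be enrolled, and here they conflict with the instructions on whom to approach. Staff working from 1.6.1 would bring in men whom 1.6.3 and 1.6.4 rule out. Staff working from 1.6.3 and 1.6.4 would turn away men whom 1.6.1 says to invite. Section 1.10.2.2 acknowledges that phase 2 adds a six-monthly rectal ultrasound beyond standard care, so it should be clear who may be asked to accept it.

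Interpretation is also at stake. Phase 2 is the longitudinal part of the study, holds at most 30 men, and looks for ultrasound change that could signal progression. Men without diagnosed cancer, low-risk men on AS and higher-grade men on WW are different populations for that question. The mix decides whether the results describe the men named in the aim and primary objective, who have known localised cancer and are on AS.

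**Working it through.** The main check is textual: take each group invited in 1.6.1 and test it against each criterion in 1.6.3 and 1.6.4.

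| Group invited in 1.6.1 | Known localised cancer, Gleason 6 or less (1.6.3) | On an AS pathway (1.6.3) | Not excluded as unsuitable for AS (1.6.4) | Admitted? |
|---|---|---|---|---|
| PI-RADS 1–2 | Normally fails: no biopsy, so no diagnosis and no grade | Not required by 1.6.1; required by 1.5.2 | Not established | No |
| Low-risk cancer, chose AS | Can meet | Meets | Meets | Yes |
| Higher grade, chose WW | Fails if higher grade means above Gleason 6 | Fails | Fails if not eligible for AS | No |

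Three readings that might reconcile the text were tried.

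1. *The words after the Gleason score in 1.6.3 might cover men with no cancer.* They cannot, because the same phrase requires the cancer to be known. Section 1.6.2 adds that entry depends on cancer grade at diagnosis, and an unbiopsied man has no grade. Electing for AS, as 1.5.2 asks, does not supply one.
2. *WW might be a form of AS.* Section 1.1.1 separates the two: men on AS are considered fit for curative treatment, while men on WW usually have comorbidities that rule it out.
3. *Higher grade is not defined by Gleason score.* This is true, but WW men fail the AS-pathway criterion at any grade.

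No reading makes 1.6.1 agree with 1.6.3 and 1.6.4. Two of the three invited groups are not admitted.

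**Scale.** The documents give no expected mix, so this is an illustration only. Inputs: a maximum of 30 men (1.6.2), an assumed share *p* of places going to PI-RADS 1–2 or WW men between 0.10 and 0.70, and all places filled.

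- Ineligible under 1.6.3 = *p* × 30: 0.10 × 30 = 3; 0.70 × 30 = 21.
- Remaining AS men = 30 − ineligible: 30 − 3 = 27; 30 − 21 = 9.

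**The case against.** The strongest defence is that recruitment text describes a pool and the criteria then filter it. On that view an invited PI-RADS 1–2 man would rarely reach enrolment. Only one sentence invites these men unconditionally, 1.5.2 narrows them to those electing for AS, and the route in 1.6.5 and 1.9.2 runs through diagnosis and the multidisciplinary meeting. This has some force: the PI-RADS part of the conflict is weaker than the WW part. It does not remove the conflict. A filter screens individuals, whereas these criteria reject two invited groups as described. For WW men, 1.6.5 goes beyond inviting them and calls them eligible.

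Other points deserve weight:

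- The opening of 1.6 and section 1.9.2 mention AS but do not say AS only. The core conflict is 1.4.2, 1.6.1, 1.6.2 and 1.6.5 against 1.6.3 and 1.6.4.
- Nothing in the protocol anchors either end of the 10% to 70% range, and 30 is a ceiling that may not be reached.
- Phase 2 compares each man with his own phase 1 baseline (1.6.10), so a mixed cohort limits how far the findings apply to AS without invalidating the within-man comparisons.
- Subgroup reporting is often left to a statistical analysis plan, which is not at hand. Separate reporting is still recommended here because the aim itself is restricted to AS men.
- The phase 2 flow chart in Appendix 3 is not shown. It might indicate what was intended, but it could not make the written criteria agree.

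**Conclusion.** The concern holds, and the protocol is wrong as written. Of the three groups invited in 1.6.1, only low-risk men on AS can satisfy 1.6.3 and 1.6.4. The PI-RADS 1–2 wording is also inconsistent between 1.6.1 and 1.5.2. This conclusion rests on the text alone. The figures of 3 to 21 ineligible men out of 30, leaving 27 to 9 AS men, depend on the assumed shares and on all places being filled. They show possible scale and carry no part of the argument. The text does not settle which population was intended. The conflict must be resolved because it decides who may enter the longitudinal phase and whom its results describe.

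**What to change.** Bring 1.4.2, 1.5.2, the opening of 1.6, 1.6.1, 1.6.2, 1.6.5 and 1.9.2 into line with 1.6.3 and 1.6.4, so that one phase 2 population is stated throughout. Which groups to follow is for the investigators to decide.

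- If PI-RADS 1–2 or WW men are kept, name them in 1.6.3 and 1.6.4, state whether PI-RADS 1–2 men must have elected for AS, and keep the overall maximum of 30. Report these men separately, and base the conclusion for the primary objective on the men with known localised cancer on AS.
- If they are not kept, remove the invitations to them.

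The cost is a wording amendment and, where a group is retained, separate tables. No patients or procedures are added. Keeping the extra groups means the AS set may fall below 30 (27 to 9 under the assumption above). Removing them leaves every place open to AS men but shrinks the recruitment pool, and 1.6.2 already warns that recruitment may be difficult.

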1.6.5 Phase 2 recruitment process

Once the initial diagnosis has been made, patients are discussed at the urology prostate multi-disciplinary meeting. A decision is made as to the most appropriate course of treatment is made and, following this, the patients attend for a consultation within a specialist prostate cancer clinic. Biopsy results and MDT outcomes are discussed and the patient is given the advised options for management. For localised low risk disease this does include active surveillance. For patients who may be less eligible for active or even deferred treatment an option of watchful waiting prior to palliative treatment being given can be offered. Providing all patients within these cohorts have had pre-biopsy MRI they are eligible for the study.

1.6.6 Participation and patient contact

Following consultation and treatment choice the eligible patients will be given an information leaflet about the study. The lead researcher will be informed of the patients who have been approached by the specialist nurse. The lead researcher will then contact the patient by telephone and invite them to participate in the study. The phase 2 recruitment pathway is provided in [appendix 3](#). Once verbal consent has been given, a mutually convenient appointment will be made and confirmed with an appointment letter.

The patient will attend for agreed appointment and a face to face consultation with the lead researcher will be undertaken to discuss the study and obtain written consent. The lead researcher will be blinded to the results of the MRI and any previous ultrasound image collection at this time to minimise undue coercion into the study, as in phase 1.

1.6.7 Image collection Phase 2

The [ultrasound examination](#) described and image collection for phase 2 is identical to that of [phase 1](#). The exception being that once the images have been collected and stored the patient will be free to leave; no further consultation, procedure or examination will be undertaken.

1.6.8 Data collection phase 2

The data collection of phase 2 is identical to that of [phase 1](#). Data collections forms utilised are attached in [Appendix 6](#) & [Appendix 7](#). The current standard and micro-ultrasound collected as part of phase 2 will be reviewed by two randomly allocated reviewers and scored as outlined above.

1.6.9 Data assessment phase 2

Once scored the documented criteria will be compared between both the standard and micro-US imaging collected during phase 2, and then compared with the previous standard and micro-US imaging [collected](#) during [phase 1](#).

1.6.10 Data analysis phase 2

The relationship between these pairs will be evaluated using Bland-Altman plots as per [phase 1](#). Scores from the ultrasound reviews will also be evaluated to determine inter-and intra-operator agreement between the randomly allocated reviewers. The phase 1 images and cine loop are the baseline data that all subsequent phase 2 examinations undertaken on that particular participant will be compared.

Any changes between the initial ultrasound scores and subsequent scores obtained during the longitudinal phase 2 study will be alerted to the lead clinical supervisor (Consultant Urologist) and the patient will be reviewed at the next MDT.

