Participants in phase 3 will then be provided with training using specific multi-parametric US techniques and will regularly score multi-parametric US examinations. Participants' confidence in knowledge and skills, related to prostate cancer evaluation using US, and how they feel this can be implemented into regular patient care will be assessed, using the same adapted survey at baseline at 6 - 12 months' post implementation.

1.4.4 Phase 4:

A fourth phase of the study is planned. Once outcomes from the initial 3 phases of the study are known the lead researcher intends to organise a national meeting where results will be presented and discussion held between the research team and other centres providing a diagnostic prostate cancer service. The aim of this event is to disseminate results and to obtain a wider understanding of

its acceptance beyond local practice. Multi-parametric ultrasound is novel and there may be resistance to wider implementation. Opportunities and barriers will be explored at this phase 4 event.

The study phases will run concurrently and will be managed by the lead researcher.

1.5 Study design and methodology – Phase 1

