1.5.10 Scan protocol

The patient will be positioned in a left sided-decubitus position or lithotomy position depending upon which is most comfortable for them. Once comfortable an ultrasound probe from a standard ultrasound machine with a scan frequency of 7.5MHz, and about the size of an adult male's index finger, is gently placed into the rectum and the prostate identified. The following images of the prostate will be obtained and saved onto the PACS system

During the ultrasound examination, the prostate gland will be scanned in a longitudinal and transverse plane from the apex to base, including seminal vesicles, and from right lateral border to

assigned to provide the consultation and biopsy as part of the standard care. Findings of the MRI will then be discussed with the patient and the patient's pathway will proceed as normal.

1.5.11 Data collection - Phase 1

Each participant will be given a unique study ID number. All images, cine loops and data for the study will be acquired and stored under this separate study ID. The data will be stored on the Hull Teaching Hospitals password protected picture archive and reporting system (PACS). A password protected database, stored in a password protected network drive of Hull Teaching Hospitals will hold the unique identifier number and will be used to record study data.

The lead researcher will randomly allocate a unique identifier number to two of the participating healthcare professionals. The reviewers will be randomly allocated to reduce bias as far as possible within a small team. Each reviewer will have their own unique identifier number known only to the lead researcher. The identity of the reviewers will be anonymised. The images and cine loops stored for the study will have no patient identifiable data on them. [Appendix 4](#) outlines the image acquisition and review pathway for phase 1 of the study.

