1.7.4 Phase 3 sample

Participants for phase 3 will be invited from the whole cohort of professionals who work within the radiology team currently involved with prostate imaging within the Hull University Teaching Hospital NHS Trust. This cohort of professionals includes urology specialised radiologists and sonographers who are involved with the production and interpretation of prostate imaging, and will also include urology consultants and urology registrars who are involved with reading and decision making from prostate imaging at multi-disciplinary team meetings. Sonographers in this cohort are radiographers who have undertaken Masters level post graduate training in medical ultrasound and specialised in specific prostate imaging. Relevant staff employed within this service will be given study information leaflets and invited to join the study. The phase 3 cohort will be a maximum of 12 staff members from varying professions.

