1.10.3.1 Risk

There is minimal risk to health care practitioners participating in phase 3 of the study. There is an established group of sonographers and radiologists providing the radiology prostate cancer assessment care pathway. There is a risk to the study of attrition of participants due to the age

demographics of the available workforce and staff relocating. There is also a risk of conflict between professional groups as knowledge and skills develop. This will be mitigated by regular communication with the study groups, led by the lead researcher and supported by the academic supervisory team as a non-involved third party. The greatest risk however is due to the lead researcher having a pivotal leadership role within the team and crucial to normal service delivery. There is a risk of unintentional bias from participants either feeling they should participate or feeling the need to please. These risks will be mitigated by open and honest communication with all team members upon recruitment and during the study.

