1.21 Appendix 6: Data collection form – Standard Ultrasound

Appendix 6: Data Collection form- Standard Ultrasound

ERUP Study Data Collection Form

Lead Researcher only	Participant number:	
	Phase 1	Phase 2

Reviewer: Please circle 1 2 3 4 5 6

Date of Review:

Imaging Reviewed:

Standard US	Date of Scan
-------------	--------------

Cine Loop Images

Please indicate findings of both longitudinal sweep and transverse sweep:

Longitudinal Sweep	Findings:	Transverse Sweep	Findings:
Opinion of prostate on review of cine loop	No apparent abnormality	Opinion of prostate on review of cine loop	No apparent abnormality
	Uncertain		Uncertain
	Normal BPH nodule (s)		Normal BPH nodule (s)
	Atypical focal area (s)		Atypical focal area (s)
If lesion identified, please indicate approximate site	Rt Lateral	If lesion identified, please indicate approximate site	Right Base
	Rt Mid		Left Base
	Central/midline		Right Mid
	Lt Mid		Left Mid
	Lt Lateral		Right Apex
			Left Apex

Approximate Prostate Volume:	
Length (cm)	
Height (cm)	
Width (cm)	
Volume:	x 0.53

Unable to calculate? State reason:

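### Phase 2 change is scored against a phase 1 baseline that may have been read by different people, so true change is mixed with reader difference and training drift

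*Protocol*

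**What the plan says.** Section 1.5.11 has the lead researcher allocate two participating professionals at random to score the phase 1 images: "The reviewers will be randomly allocated to reduce bias as far as possible within a small team". For phase 2, section 1.6.8 states "The data collection of phase 2 is identical to that of" phase 1, and that the current standard and micro-ultrasound images "collected as part of phase 2 will be reviewed by two randomly allocated reviewers".

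Sections 1.6.9 and 1.6.10 compare these results with the phase 1 imaging, which is the baseline for every later examination of that man. Section 1.6.10 continues: "Any changes between the initial ultrasound scores and subsequent scores obtained during the longitudinal phase 2 study will be alerted" to the consultant urologist, with review at the next MDT meeting. Section 1.6 adds an offer of MRI.

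The forms in Appendices 6 and 7 carry six reader codes: "Reviewer: Please circle 1 2 3 4 5 6". Section 1.7.4 sets a ceiling on the staff cohort: "The phase 3 cohort will be a maximum of 12 staff members from varying professions". Section 1.4.3.1 describes skills that develop during the study: "Participants in phase 3 will then be provided with training using specific multi-parametric US techniques and will regularly score multi-parametric US examinations". Section 1.10.3.1 expects some staff to leave: "There is a risk to the study of attrition of participants".

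**The concern.** Section 1.4.2 gives phase 2 the task of finding out whether changes at repeat ultrasound can indicate progression. The measure for this is a within-man difference in score. If the baseline and follow-up scores come from different people, that difference has three parts: true change in the gland, the difference in threshold between readers, and drift as readers are trained and gain experience. Random allocation evens out the reader part on average over many men. It does not do so within one man, and it does nothing about drift, which runs in calendar time like follow-up itself.

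A stable gland can then appear changed because a stricter or later-trained reader scored it, and a real change can be masked in the same way. With at most 30 men (section 1.6.2), a later model could not reliably separate these parts. Apparent changes also have a practical cost, since they lead to MDT review and an MRI offer in a study motivated by scarce MRI capacity.

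**Working it through.** The protocol states no agreement, power or error figure on this point, so there is nothing of its own to reproduce. Two calculations bear on it.

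**1. How often the readers would differ**

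Inputs: two readers per scan (1.5.11, 1.6.8) and six reader codes (Appendices 6 and 7). Assumption: the phase 2 pair is an independent random draw. The number of possible pairs is C(6,2) = 15.

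- Same pair as baseline: 1/15 = 6.7%.
- One reader shared: 2 × (6 − 2)/15 = 8/15 = 53.3%.
- No reader shared: C(4,2)/15 = 6/15 = 40.0%.
- At least one reader differs: 1 − 1/15 = 14/15 = 93.3%.

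The same-pair probability would be 1/6 = 16.7% with four readers, and 1/66 = 1.5% with the ceiling of 12 staff.

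**2. What a different reader does to the score of an unchanged gland**

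Section 1.5.4 says that little is known about the spread of the ultrasound scores, so every input here is an assumption:

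- latent true score with SD 1, the same at both times;
- cut points at −1.2, −0.4, 0.4 and 1.2, giving a 5-point score;
- within-reader SD 0.3;
- between-reader SD 0.3, 0.5 or 0.7;
- no drift.

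Score = category of (true value + reader effect + noise). The result is the proportion with any change in score, from 200,000 simulated glands.

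| Between-reader SD | One reader: same | One reader: different | Two-reader mean: same pair | Two-reader mean: pair redrawn from six |
|---|---|---|---|---|
| 0.3 | 0.36 | 0.48 | 0.51 | 0.58 |
| 0.5 | 0.35 | 0.57 | 0.50 | 0.64 |
| 0.7 | 0.33 | 0.63 | 0.49 | 0.68–0.69 |

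The last cell is a range because separate runs differed in the second decimal. The excess is 12 to 30 points for a single reader and about 7 to 20 points for the mean. Part of the gap arises because the single-reader column assumes that the reader has definitely changed, whereas a redrawn pair sometimes shares a reader with baseline. The protocol does not say how the two scores are combined, so both versions are shown.

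With no between-reader effect, the single-reader rate is about 0.37 either way, and switching adds nothing.

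A second set of assumptions (cut points at quintiles, readers redrawn from six) points the same way for a single reader: 0.38 to 0.47 with between-reader and within-reader SD both 0.3, 0.37 to 0.54 with SDs 0.5 and 0.3, and 0.41 to 0.62 with SDs 0.8 and 0.4.

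**The case against.** **The premise is partly inferred.** The protocol never says that a new pair is drawn for each scan rather than once per man. The image review pathways in Appendices 4 and 5 survive only as headings and might settle it. Section 1.6.10 also names the phase 1 images, not only their scores, as the baseline, and it promises intra-operator agreement, which needs repeat reads by one person. This stands as a limit on certainty. It supplies no safeguard, because no readable sentence assigns the same readers or orders a re-read, and the alert in 1.6.10 is worded in terms of scores.

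**Rotating readers is a legitimate choice.** Random allocation is there to reduce bias, operator variability is an objective (1.3.2), and a surveillance tool that works only with a fixed reader would be of little routine use. That is a good reason to keep random allocation in phase 1. It is a weaker reason in a first test of whether change can be seen at all. The planned agreement analysis is not linked to the change comparison.

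**The harm is bounded.** A flagged change goes to MDT review and an MRI offer, and section 1.10.2.2 ties biopsy to a change on MRI. A reader might infer that switching readers sends stable men to biopsy. The protocol does not support that, because MRI comes in between. Unnecessary review and MRI remain a cost.

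**Most apparent change would remain.** Even with the same pair, about half of unchanged glands show some change in the two-reader mean under these assumptions, because any difference counts. This stands.

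**Conclusion.** The point holds as a design weakness that should be corrected. On the readable text, within-man change in phase 2 is not separated from who read the images and when. If pairs are redrawn from six readers, at least one differs from baseline in 93% of comparisons. The consequence depends on reader agreement, which is unknown: about 7 to 20 extra points of apparent change for a two-reader mean under the stated assumptions, more for a single reader, and none if readers do not differ systematically. Drift would add to this and has not been quantified.

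Two stronger readings are tempting. One is that the protocol definitely redraws readers at every scan; the unit of the draw is not stated, and the relevant flow charts are not shown. The other is that a change of reader is itself recorded as a change in the prostate; it registers only when the two readers score differently. Given these limits, the bounded harm and the proof-of-concept purpose, this is not a fault that invalidates the study.

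**What to change.** Keep random allocation in phase 1. In sections 1.6.8 and 1.6.9:

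- State the unit of allocation, and assign each man's phase 2 images to the two readers who scored his phase 1 images.
- For the phase 2 change analysis, have those readers re-score the anonymised phase 1 set together with the follow-up set, in random order and with dates masked. The scan date and phase fields on the forms would need to be hidden during this reading. Keeping the same readers deals with the difference between readers; reading both sets together deals with drift.
- If a reader has left, the replacement scores both sets.

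The re-reads would also supply the repeat readings that the promised intra-operator analysis needs.

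Cost: protocol wording, an allocation list and reading time, with no new scans or staff. One batch re-read of the baseline sets is at most 30 men × 2 readers × 2 modalities = 120 forms. Follow-up sets already scored for alerts and read again in that batch would add to this. Re-reading the baseline at each of three assumed follow-up visits would take 30 × 3 × 2 × 2 = 360 extra forms. There is some risk that a reader recalls a case, which masking and random order limit.

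Within-reader noise remains, so false change is reduced and not removed. Separately, sections 1.6, 1.6.10 and 1.10.2.2 describe the trigger for an alert and what follows in different terms. The investigators should reconcile them.
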